The primary outcome is HbA1c level at 12 months of follow-up. HbA1c will be measured by obtaining blood specimens, physical activity will be measured by the 7-day physical activity recall, diet will be measured by the Block food frequency questionnaire, medication adherence will be measured by electronic medication event monitoring system, and self-monitoring of blood glucose will be measured by glucometer downloads.

RESEARCH DESIGN AND METHODS

Study Overview: We propose to test the efficacy of a combined telephone-delivered, diabetes knowledge/information and motivation/behavioral skills training intervention in high risk Blacks with poorly controlled T2DM (HbA1c $\geq 9\%$). Our aim is to determine whether a separate or combined telephone-delivered diabetes knowledge/information and motivation/behavioral skills training intervention will lead to greater improvements in glycemic control compared to usual care using a 2x2 factorial design. 232 African Americans with T2DM will be randomized to one of four groups: 1) telephone-delivered diabetes knowledge/information; 2) telephone-delivered motivation/behavioral skills training; 3) combined telephone-delivered diabetes knowledge/information and motivation/behavioral skills training; and 4) usual care. The proposed patient-level intervention is based on the information-motivation-behavioral skills model and provides information, motivation, and behavioral skills training. The usual care group will receive weekly telephone-delivered general health education lasting 30 minutes every week for 12 weeks to control for attention. Study assessments will be performed by a blinded research assistant at baseline, 3, 6, and 12 months of follow-up. The primary outcome is HbA1c level at 12 months of follow-up.

Study Population & Recruitment plan:

Study clinics: The study sites for this study are primarily the MUSC general medicine, endocrine, family medicine, and community primary care clinics. The study will be conducted out of the MUSC Center for Health Disparities Research.

Participant Payment: Participants will receive \$25 for completion of baseline assessment materials, \$25 for the 3-month assessment, \$25 for the 6-month assessment, and \$25 for completion of the 12-month follow-up assessment.

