The proposed sample size calculations are based on the premise that we will test three hypotheses in this 2x2 factorial design: 1) the overall effect of diabetes knowledge/information versus no diabetes knowledge/information, 2) the overall effect of motivation/behavioral skills versus no motivation/behavioral skills, and 3) the effect of the combined interventions. The primary endpoint for testing these hypotheses is the 12 month HbA1c value. Power calculations are based on the comparison of group means when accounting for

the baseline value (ANCOVA) with normally distributed data. The model will have an intercept plus three coefficients: beta1 for the effect of diabetes knowledge/information, beta2 for the effect of motivation/behavioral skills and beta3 for the interaction effect. The study has 85% power (2-sided type I error rate of 0.05) to detect a clinically relevant difference of 1 percentage point in the 12-month HbA1c (assuming a common standard deviation of 1.5). The clinically relevant difference in HbA1c at 12 months is based upon the findings of a previous RCT of telephone-delivered diabetes intervention (Piette et. al., 2001) and our pilot study. Sample size estimation is based on a 2x2 factorial design and takes into account the potential interaction between the diabetes knowledge/information and motivation/behavioral skills intervention. A total of 42 subjects per arm is required to achieve 85% power (type I error rate of 0.05) to detect a clinically relevant difference of 1 percentage point in the 12-month HbA1c (assuming a common standard deviation of 1.5). Because testing for an interaction can greatly increase the sample size and since interaction is not our specific interest, we chose to ensure that we have adequate power to detect main effects in the presence of an interaction. Thus the total number of subjects required for randomization is 168 subjects (42 per treatment arm). The total sample size is inflated by a factor of 1.38 to account for an anticipated 15% attrition rate in an intent-to-treat analysis (Friedman et al, 2003). Thus a total of 232 subjects will be randomized into this study.

Data Analysis

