Primary and secondary data analyses will be conducted using the intent-to-treat population. This population is defined as all randomized subjects. Sensitivity analyses will be conducted by repeating the proposed analyses using the per protocol population which is defined as all randomized subjects who complete 12 months of follow up. **Primary Objective:** To test the separate and combined efficacy of a *telephone-delivered diabetes knowledge/information and motivation/behavioral skills training intervention* in improving HbA1c levels in Blacks with T2DM using a 2x2 factorial design. Preliminary analyses will be conducted to assess the similarity of the treatment arms based on collected variables. Univariate descriptive statistics and frequency distributions will be calculated, as appropriate for all variables along with two-sided 95% confidence intervals when appropriate. Study discontinuation (attrition) rates will be estimated for each group. The primary framework for analysis is analysis of covariance. Twelve-month HbA1c measurements (dependent variable) will be compared between treatment arms using a model-based approach with telephone-delivered *diabetes knowledge/information*, telephone-delivered *motivation/behavioral skills training* and the interaction of the two factors in the model along with baseline HbA1c as a covariate. A global test approach will be implemented in order to preserve the type I error rate (*Green, Liu and O'Sullivan, 2002*). A mixed model repeated measures analysis of covariance will be conducted as a secondary analysis to assess the difference in HbA1c levels over time. The model will include telephone-delivered *diabetes knowledge/information* and telephone-delivered *motivation/behavioral skills training* and the interaction of the two as factors in the model along with baseline HbA1c as a covariate. A similar analysis plan using a global test approach as describe above will be implemented. If the interaction is not significant, it will be dropped from the model. Covariance structures will be assessed during the model-fitting process using SAS PROC MIXED.

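### Dropping a non-significant interaction from the secondary repeated-measures HbA1c model lets an unpowered test decide what is estimated for one component versus usual care

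*Protocol*

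**What the plan says.** The Data Analysis section fits the primary 12-month ANCOVA with both factors, their interaction and baseline HbA1c. It then adds a further model: "A mixed model repeated measures analysis of covariance will be conducted as a secondary analysis to assess the difference in HbA1c levels over time". This model has the same factors, interaction and covariate, and a similar global test approach. For it the protocol adds: "If the interaction is not significant, it will be dropped from the model". The sentence gives no significance level.

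The Sample Size and Power section explains that the interaction was not a sizing target: "Because testing for an interaction can greatly increase the sample size and since interaction is not our specific interest", the authors write, "we chose to ensure that we have adequate power to detect main effects in the presence of an interaction". It names three hypotheses: the overall effect of each component, and the effect of the combination.

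The Study Overview words the aim as arm comparisons: "Our aim is to determine whether a separate or combined telephone-delivered diabetes knowledge/information and motivation/behavioral skills training intervention will lead to greater improvements", and names the comparator: "will lead to greater improvements in glycemic control compared to usual care using a 2x2 factorial design".

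**The concern.** The protocol declines to power the interaction test, yet that test chooses the secondary model. A non-significant result from a weak test is not evidence that the components act additively.

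The choice changes what is estimated for the separate part of the aim. In the full model, knowledge alone versus usual care compares those two arms. In the reduced model, the fitted difference between the same arms is the effect of knowledge averaged over patients with and without skills training. If the components interact, the reported interval is off centre for the single-arm question and too narrow. The data decide which of the two effects it describes. A reader could then see two different figures for the same two arms, from the primary ANCOVA and from the secondary model, with the secondary one looking more precise than it is.

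**Working it through.** **Inputs from the protocol.** Two-sided alpha 0.05, 85% power, difference 1 point, common SD 1.5, 42 per arm (Sample Size and Power); 58 randomized per arm and 15% attrition (Attrition and Retention); visits at 3, 6 and 12 months.

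**Assumptions.** Residual SD 1.5 at each visit; pre-test at 0.05; cumulative loss 5/10/15% at the three visits; effect constant over visits; within-patient correlation 0.4 to 0.8, compound symmetry (CS) or AR(1); interaction 0.25 to 1.0 point. The protocol gives none of the correlation, the loss before 12 months or the interaction size.

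**The plan's own figure.** For one arm against one arm, n = 2 × 1.5² × (1.960 + 1.036)² / 1² = 40.4, so 41 per arm. With the t distribution, 42 per arm gives 85.5% power. The stated 42 is thus reproduced as a single-arm versus single-arm comparison. A pooled main effect (84 versus 84) would have about 99% power.

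**What dropping the term does.** In a balanced 2×2, write the arm means as m00 (usual care), m10, m01 and m11.
- Overall effect: M = (m10 + m11 − m00 − m01)/2, variance v.
- Interaction: I = m11 − m10 − m01 + m00, variance 4v, independent of M.
- One component alone versus usual care: m10 − m00 = M − I/2, variance 2v.

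The reduced model replaces M − I/2 with M. The shift is half the interaction whatever the SD, and the standard error falls by √2 = 1.41. Combined versus usual care does not change, because the two overall effects sum to m11 − m00.

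**Single visit, 42 per arm.** SE(I) = 2 × 1.5/√42 = 0.463.
- I = 0.5: ratio 1.08, power about 19%, so dropped in 81%; coverage for one component alone about 82%.
- I = 1.0: ratio 2.16, power about 58%, so dropped in 42%; coverage about 73%.

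**Repeated measures, worked case (CS, correlation 0.6).** A patient with m visits contributes m / [2.25 × (1 + 0.6(m − 1))]: 0.606, 0.556 and 0.444 for m = 3, 2 and 1. With 58 per arm, 49.3 patients have three visits, 2.9 have two and 2.9 have one. Information per arm = 49.3 × 0.606 + 2.9 × 0.556 + 2.9 × 0.444 = 32.8, so v = 0.0305 and √v = 0.175.
- Half-width for one component alone: 1.96 × √(2v) = 0.484 in the full model, 1.96 × √v = 0.342 in the reduced model.
- At I = 0.5, 0.5/(2 × 0.175) = 1.43, so the term is dropped in about 70% of trials.
- When dropped, the interval is off centre by 0.25 = 1.43 × √v, so it covers about 70%. When kept, it covers about 92%.
- Overall: 0.70 × 0.70 + 0.30 × 0.92 = 0.77.

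**Range over the six correlation settings.**

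| True interaction (points) | Dropped | Coverage of nominal 95% interval, one component alone |
|---|---|---|
| 0 | 95% | about 93.5% |
| 0.25 | 87–90% | 87–89% |
| 0.5 | 62–74% | 74–78% |
| 0.75 | 30–49% | 73–76% |
| 1.0 | 9–25% | 79–89% |

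The full-model single-arm contrast and the overall effect cover 95.0% throughout. A simulation with estimated CS covariance and random dropout agreed: at I = 0.5 and correlations 0.4 / 0.8, the term was dropped in 64% / 75% and coverage was 76% / 80%. In that simulation the drop rule left coverage at 0.947–0.961 for the overall effects and 0.943–0.956 for combined versus usual care.

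**The case against.** The strongest reply is that the three named hypotheses are the two overall effects and the combination, and that these survive the rule. No sentence assigns the single-arm contrast to the repeated-measures model. That is correct, and it limits the point to the separate-versus-usual-care reading. The reading is still a fair one: the Study Overview states the aim that way, and 42 per arm matches a single-arm comparison.

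Second, the protocol gives no coding. Under effect coding the main-effect coefficient is the overall effect whether or not the interaction stays. That is true of the coefficient. The fitted difference between a single-component arm and usual care still moves by half the interaction under any coding.

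Third, the global test applies here too, and the protocol does not describe its steps. It could affect when a reduced-model interval is reported. It does not correct the shift in what that interval estimates.

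Fourth, the figures rest on assumed inputs, including an effect constant over visits in a model meant to examine change over time. This stands: the percentages are illustrative, while the half-interaction shift is not.

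Finally, an SAP that was not available may specify the reported contrasts. The drop rule itself is stated in the protocol, and only that rule is criticised here.

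**Conclusion.** The concern holds and is minor. The protocol fixes a data-dependent rule, driven by a test it says it did not size for, that changes the estimate of one component alone versus usual care in the secondary HbA1c model. For true interactions of 0.25 to 1.0 point, the nominal 95% interval for that contrast covers between 73% and 89% under the stated assumptions. With no interaction the loss is trivial. A residual SD below 1.5 after baseline adjustment, or effects that vary by visit, would change these figures.

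The primary ANCOVA as written keeps the interaction, so sound single-arm contrasts at 12 months remain available from it.

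**What to change.** Delete the sentence that drops the interaction. State that the interaction stays in the repeated-measures model whatever its p-value, and keep the global test. From that one model report, separately labelled: the overall effect of each component, each single-component arm versus usual care, combined versus usual care, and the interaction with its 95% confidence interval.

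The cost is wording and one degree of freedom, with no extra patients. Overall effects and combined versus usual care lose essentially no precision. Single-arm intervals are wider than the reduced model would show: about ±0.42 to 0.52 instead of ±0.30 to 0.37 with repeated measures. For a single visit with 49 per arm (58 × 0.85), they are 1.96 × 1.5 × √(2/49) = ±0.59 instead of 1.96 × 1.5/√49 = ±0.42.

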February 20, 2009

NCT00929838

Protocol: Telephone Delivered Behavioral Skills Intervention for Blacks With T2DM

Principle Investigator: [name], MS

A: SPECIFIC AIMS

Blacks (African Americans) with Type 2 diabetes (T2DM) have higher prevalence of diabetes, poorer metabolic control, and greater risk for complications and death compared to Whites (NIH2002). Poor outcomes in Blacks with T2DM can be attributed to patient, provider, and health systems level factors (Egede 2005). Provider and health system factors account for <10% of variance in major diabetes outcomes including hemoglobin A1c (HbA1c), lipid control, and resource use (Hofer 1999, Krein 2002). Key differences appear to be at the patient level (Egede 2005). Of the patient level factors, consistent differences between Blacks and Whites with T2DM have been found in diabetes knowledge, self-management skills, empowerment, and perceived control (Egede 2005, Anderson 1991, Harris 1993, Egede 2004, Jack 2004, Egede 2003). This study provides a unique opportunity to address this gap in the literature. Using a 2x2 factorial design, this study will test the efficacy of separate and *combined telephone-delivered, diabetes knowledge/information and motivation/behavioral skills training intervention* in high risk Blacks with poorly controlled T2DM (HbA1c $\geq 9\%$).

Primary Objective

To test the separate and combined efficacy of a *telephone-delivered diabetes knowledge/information and motivation/behavioral skills training intervention* in improving HbA1c levels in Blacks with T2DM using a 2x2 factorial design.

Secondary Objectives

1. To determine whether patients randomized to the *telephone-delivered diabetes knowledge/information intervention, the telephone-delivered motivation/behavioral skills training intervention, or the combined intervention* will have greater improvement in physical activity, diet, medication adherence, and self-monitoring of blood glucose at 12 months of follow-up compared to usual care.
2. To determine the cost-effectiveness of each telephone intervention separately, and then in combination.

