1. Research Material & Data: Sources of research material include medical history, research questionnaires, blood pressure readings, and blood specimens. The questionnaires will obtain information about demographics, clinical history, diabetes self-care, resource use, depression, and quality of life. Patients will provide ~ 10 cc of blood for laboratory testing.

2. Linkages to Subjects: Subjects will provide identifying information in addition to research data. Paper documents pertaining to this study will be stored in locked file cabinets in both the clinical center and the data management center, and data will be entered into secure, password-protected databases developed for this study. A database of name, contact address, telephone number, and other research identification numbers will be stored separate from the study database, for purposes of audit by the sponsor (NIH) and MUSC IRB, if necessary. Access to study data will be limited to research personnel.

3. Collection of Data and Specimens:

Participants will be randomized to one of four groups: 1) telephone-delivered diabetes knowledge/information; 2) telephone-delivered motivation/behavioral skills training; 3) combined telephone-delivered diabetes knowledge/information and motivation/behavioral skills training; and 4) usual care.

c. Potential Risks

Potential risks to the patient include possible violation of the patient's privacy, discomfort with questions on the research questionnaire, discomfort and bleeding from blood draws, discomfort with BP measurement, and psychological distress. Details on how these risks will be minimized are discussed under adequacy of protection against risks below.

ADEQUACY OF PROTECTION AGAINST RISKS

Recruitment and Informed Consent

We will use two complementary approaches to identify eligible study subjects. The first method will consist of systematic identification of patients with type 2 diabetes. The second method will consist of referrals

from primary care providers, other clinic staff such as nurses, or patients themselves in response to recruitment flyers for the study.

Protection against Risk

A. Patients will be protected against potential risks as follows:

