1. Psychological Distress: Because we will be administering a questionnaire that measures the presence of depression, we will take several steps to ensure the safety of all research participants. RAs will be trained by the PI to identify patients who meet criteria for depression on the PHQ-9. Subjects' who screen positive for depression will be notified during the visit and verbally instructed to seek care from their primary health care provider (PCP). They will also be given the 24-hour MUSC crisis psychiatry telephone service and told to call if they experience acute worsening of symptoms before they can be seen by their PCP.

2. Venipuncture (blood drawing): To reduce the risks of discomfort and bruising, venipuncture will be performed by trained personnel. To reduce the risk of fainting, blood will be drawn while subjects are in a seated position. The amount of blood that will be drawn, approximately 10cc, is not considered to pose a health risk for most adults. .

3. Blood Pressure Measurement: To lessen any associated risks, blood pressure measurements will be performed only by trained personnel utilizing a standardized protocol. Subjects with elevated blood pressure will be advised to contact their primary care provider. Those with potentially life threatening blood pressure readings will be sent to a local emergency room for treatment.

4. Administration of Research Questionnaires: Some participants might be offended by detailed questions about emotional or physical health status and impairment, and healthcare utilization. All participants will be informed at the outset that they may terminate participation at any point. Our past research suggests that data collection using these measures can be conducted without undue psychological distress or exacerbation of symptoms among study participants.

5. Unknown risks: Subject participation in research may have other unknown risks. The researchers will advise subjects if they learn of emerging information that might alter subjects' decisions to participate in this study.

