3. POTENTIAL BENEFITS OF THE PROPOSED RESEARCH TO THE SUBJECTS AND OTHERS

The intervention is expected to benefit patients, by increasing their knowledge of diabetes, activating and empowering them to better care for their diabetes, improving blood glucose and blood pressure control, and reducing their risk developing complications of diabetes. Patients in the usual care group will benefit by increasing their general health knowledge.

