5. DATA AND SAFETY MONITORING PLAN

The data and safety monitoring plan will include an internal Data Safety Monitoring Committee (DSMC) and the institutional IRB. The purpose of the DSMC and IRB are to ensure the safety of participants and the validity and integrity of the data. Summaries of adverse events reports or patient safety concerns raised by the IRB will be made to NIH in the yearly progress unless the nature of a particular event is such that it bears reporting to NIH immediately.

DSMC: The internal DSMC will consist of the PI, biostatistician, co-investigators/consultants on the proposal, and a designated medical monitor. The functions of the DSMC will include: 1) provide scientific oversight; 2) review all adverse effects or complications related to the study; 3) monitor accrual; 4) review summary reports relating to compliance with protocol requirements; and 5) provide advice on resource allocation. The DSMC will meet quarterly and as necessary by telephone. The recommendations of the DSMC will be reviewed and the PI will take appropriate corrective actions as needed.

Institutional IRB: The IRB will review and approve the funded protocol, review patient and provider consent forms, ensure protection of patient privacy and safety, and monitor the study on an ongoing basis. Adverse events will be reported to the IRB as they occur. Annual reports to the IRB will indicate accrual rate, adverse events, new findings that may influence continuation of the study, and reports of the DSMB.

INCLUSION OF CHILDREN

Children (ages 18-21) are included in this study. Children under the age of 18 years are excluded because type 2 diabetes is not common in younger aged children. Based on our study clinic demographics, we estimate that children 18-21 years will comprise ~5% of the sample.

INCLUSION OF WOMEN

Both men and women will be included in this study. Based on our study clinic demographics, we estimate that women will constitute 50% of the sample.

INCLUSION OF MINORITY GROUPS

Only minority adults (African Americans) are included in this study. This is justified because of the high burden of diabetes and its complication in African Americans, and the paucity of data on effective interventions in this population.

BIBLIOGRAPHY & REFERENCES CITED

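### The protocol names no risk from the interventions and plans no systematic capture of hypoglycemia, a foreseeable harm for participants who take glucose-lowering drugs

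*Protocol*

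**What the plan says.** **Risks.** After loss of privacy, the protocol's Potential Risks paragraph lists "discomfort with questions on the research questionnaire, discomfort and bleeding from blood draws, discomfort with BP measurement, and psychological distress". Protection against Risk gives safeguards for these and adds: "Subject participation in research may have other unknown risks". Hypoglycemia appears nowhere in the protocol.

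**Intended effects.** The first secondary objective is that participants in the three intervention arms "will have greater improvement in physical activity, diet, medication adherence, and self-monitoring of blood glucose at 12 months of follow-up compared to usual care". The Potential Benefits section expects the intervention to help by "improving blood glucose and blood pressure control, and reducing their risk developing complications of diabetes".

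**Glucose meters.** Their only stated use is behavioral: "self-monitoring of blood glucose will be measured by glucometer downloads".

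**Adverse events.** Protection against Risk (item B) and the Data and Safety Monitoring Plan send adverse events to the IRB, with summaries to NIH. The internal committee is to "review all adverse effects or complications related to the study". No hypoglycemic event is defined, and no question about one is described.

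**Visits and calls.** Under Study Overview, a blinded research assistant does the assessments at baseline, 3, 6 and 12 months. The usual care arm receives weekly general health education calls for 12 weeks as an attention control.

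**The concern.** The protocol states the glucose-lowering effect it hopes for but not that effect's adverse counterpart. Better adherence and tighter control can produce low glucose in people who take glucose-lowering drugs. Because this can be foreseen, an item on unknown risks does not cover it.

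The practical loss is in data collection. Without a planned question, hypoglycemia is recorded only if a participant happens to mention it and someone treats it as an adverse event. Three arms have weekly calls about diabetes, and the fourth has weekly calls about general health. Participants may be prompted to mention low glucose in the former and not in the latter, so spontaneous counts could differ by arm for reasons unrelated to true frequency. The trial would then report HbA1c and cost-effectiveness from systematic measurement, with no comparable measure of a related harm. An analysis plan could add a table later, but it could not recover answers that were never collected.

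**Working it through.** **Step 1: source of each named risk.**

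| Named risk | Source |
|---|---|
| Privacy | Data handling |
| Questionnaire discomfort | Assessment |
| Blood draw | Assessment |
| Blood pressure measurement | Assessment |
| Psychological distress | Assessment (safeguard tied to the depression questionnaire) |
| Unknown risks | Unspecified |

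None comes from the education or skills calls.

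**Step 2: who is exposed.** Three arms of 58 receive an active intervention: 3 x 58 = 174 of 232. That is an upper limit on the number at added risk. Entry requires an oral drug for diabetes, hypertension or hyperlipidemia, so some participants may take no glucose-lowering drug. The protocol gives no drug mix.

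**Step 3: the plan's own figures.** The point disputes none of them. For a difference of 1 and an SD of 1.5, two-sided 0.05 and 85% power:
- Normal approximation: 2 x (1.960 + 1.036)^2 x 1.5^2 / 1^2 = 40.4, so 41 per arm.
- With the t distribution, 42 per arm gives power 0.855, which matches the stated 42.
- Inflation: 1 / 0.85^2 = 1.384, and 168 x 1.38 = 231.8, so 232 (58 per arm).
- After 15% attrition: 58 x 0.85 = 49.3, taken as 49 evaluable per arm.

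**Step 4: precision of a comparison by arm.** The protocol gives no hypoglycemia rate, so the rates here are assumptions. For 15% versus 5% reporting any episode:
- Single arms, 49 versus 49: SE = sqrt(0.15 x 0.85/49 + 0.05 x 0.95/49) = 0.060. The 95% interval is 0.10 +/- 1.96 x 0.060, about -2 to +22 points.
- Factorial margin, 98 versus 98: SE = sqrt(0.15 x 0.85/98 + 0.05 x 0.95/98) = 0.042, giving about +2 to +18 points.

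**Step 5: range over assumed rates.** The rate needed in the other group for 80% power (pooled two-proportion normal test, two-sided 0.05, all randomized participants evaluable) is:

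| Comparison-group rate | 58 vs 58 | 116 vs 116 (margin) |
|---|---|---|
| 2% | 17.2% | 11.1% |
| 5% | 22.9% | 16.3% |
| 10% | 30.8% | 23.7% |
| 20% | 44.1% | 36.5% |

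The detectable excess is about 15 to 24 points between single arms and 9 to 17 points on a margin. If nobody among 58 reports an episode, the one-sided 95% upper bound is 1 - 0.05^(1/58) = 5.0%; for 116 it is 2.5%.

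**Step 6: why meter data cannot carry the comparison.** If each reading is low with probability r, independently, the chance of at least one low reading in m readings is 1 - (1 - r)^m, which rises with m. Self-monitoring is an outcome that the interventions aim to increase, so the arms may differ on this measure even with equal r. A rate per 100 readings removes the dependence on m, but not on when participants choose to test.

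**The case against.** The case against has real force.

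- **Adverse events are reported.** The IRB reporting sentences are not limited to listed or related events, so a reported episode would be seen. A reader might infer that sites have no reason to record hypoglycemia; the documents do not support that. What is missing is planned, uniform elicitation.
- **The size of the risk is not in the documents.** A reader might infer that hypoglycemia is the main expected harm, or that everyone is on glucose-lowering treatment. Entry HbA1c is at least 9%, the interventions are telephone education and skills training, and a glucose-lowering drug is not required. Foreseeable for those who take such drugs is as far as the text goes.
- **The 1 point is not a treatment target.** The power statement uses it "to detect a clinically relevant difference of 1 percentage point in the 12-month HbA1c (assuming a common standard deviation of 1.5". It is a between-group planning difference, and nothing says the interventions are to cut each participant's HbA1c by 1 point.
- **Contact and staff are matched.** Usual care has weekly calls too, and each educator serves all four arms. Any reporting imbalance would have to come from call content; it is plausible but not shown.
- **The instruments are not shown.** Domains such as diabetes self-care, medical history and resource use might include a hypoglycemia item. The protocol text does not say so.
- **Tables by arm may be left to an analysis plan, and patient safety procedures are a Year 1 activity in the timeline.** Both are true, so the absence of a table is not the finding. The risk list is set in this protocol, however, and it describes no question that would supply the data.

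What survives is narrow: no intervention-related risk is named, and no systematic capture is described.

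**Conclusion.** The point holds in this limited form. The protocol's named risks come from research procedures and privacy, plus an unspecified item, and none comes from the interventions. Hypoglycemia is foreseeable in participants taking glucose-lowering drugs, but it is neither listed nor systematically collected. General adverse event reporting exists, but it is passive for this event and may be uneven across arms.

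This is an inexpensive improvement and not an error that threatens the primary analysis; no stated figure changes. Its size cannot be derived from the documents, because they give neither an event rate nor the share of participants on glucose-lowering drugs. A reader might infer that routine capture would rule out a large excess. On the assumed 15% versus 5% with 49 per arm, the interval of about -2 to +22 points does not exclude even a 20-point excess. Only very large excesses could be excluded, so the comparison would be descriptive. The conclusion assumes that the questionnaires contain no standard hypoglycemia item. If they do, what remains is to add the risk to the list and to use that item as described below.

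**What to change.** 1. Add hypoglycemia to Potential Risks and to the matching safeguards, and check that the participant information agrees.
2. Have the blinded research assistant put the same standard question on hypoglycemic episodes to participants in all four arms at the existing 3-, 6- and 12-month visits. Fix the wording and the recall period in advance; the intervals are 3, 3 and 6 months.
3. Give the safety committee a table of the answers by arm and by factorial margin, with confidence intervals, labelled as a descriptive safety outcome.
4. Optionally report low readings per 100 readings from the existing downloads, below a level that the investigators prespecify. Label this as supportive only, because the interventions may change both how often and when participants test. Do not use the proportion with any low reading as the comparison.

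The cost is one item at visits already planned, one table and a wording edit. It needs no extra visit, no larger sample and no change to treatment. Two limits remain: precision is low, and an identical question equalizes the asking but not participants' ability to recognize an episode, which diabetes education may itself improve.
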